8.2 Randomization, Visit 2 (Day 1)

Subjects will return to the study site at Visit 2 (Day 1) for the performance of study related procedures, randomization and dispensing of study drug and lubricant. All baseline procedures are to be performed prior to the first dose of study drug. After Visit 2, study subjects will be instructed to identify the most appropriate time for dosing each day (ie, time of day most likely to be associated with highest compliance and convenience). Once the time of dosing is established, every effort should be made to take the study drug at approximately the same time each day.

The following measurements and/or evaluations will be made and recorded in the eCRF:

- Record any changes in prior therapy since screening
- Obtain urine sample for urinalysis, dipstick, and urine markers of bone metabolism. Dipstick assessment should be performed prior to the next procedure
- Assess inclusion/exclusion criteria (including results of safety laboratory tests, PAP smear, and endometrial biopsy obtained at screening)
- Assess for AEs
- Assess symptoms of VVA
- Assess FSFI
- Assess UDI-6
- Measure vital signs (BP, pulse rate, and oral temperature performed after subject is in seated or in a recumbent position ≥ 3 minutes) including weight
- Perform physical examination
- Perform breast examination
- Perform gynecological examination

- Measure vaginal pH
- Obtain vaginal smear for assessment of maturation index
- Assess VHI
- Assess VuHI
- Obtain vulvo-vaginal imaging (optional)
- Obtain blood samples for safety laboratory tests, hormone levels, and serum markers of bone metabolism
- Dispense eDiary and instruct the subject on how to use it
- Contact IxRS to randomize the subject
- Dispense study medication and lubricant
- Reinforce compliance with study medication

8.3 Treatment Period, Visit 3 (Week 4) through Visit 5 (Week 12)

8.3.1 Visit 3 (Week 4) and Visit 4 (Week 8) Procedures

The following measurements and/or evaluations will be made and recorded in the eCRF:

- Record any changes in concomitant therapy
- Assess for AEs
- Assess symptoms of VVA
- Assess FFSI
- Assess UDI-6
- Measure vital signs (BP, pulse rate, and oral temperature performed after subject is in seated or in a recumbent position ≥ 3 minutes) including weight
- Measure vaginal pH
- Obtain vaginal smear for assessment of maturation index
- Assess VHI
- Assess VuHI
- Assess eDiary compliance
- Assess study medication returned and assess compliance with study medication
- Dispense study medication assigned by IxRS and lubricant
- Reinforce compliance with study medication

8.3.2 Visit 5 (Week 12) End of Study Procedures

The following measurements and/or evaluations will be made and recorded in the eCRF:

- Record concomitant therapy
- Assess for AEs
- Assess symptoms of VVA

- Assess FSFI
- Assess UDI-6
- Measure vital signs (BP, pulse rate, and oral temperature performed after subject is in seated or in a recumbent position ≥ 3 minutes) including weight
- Perform physical examination
- Perform breast examination
- Perform gynecological examination
- Measure vaginal pH
- Obtain vaginal smear for assessment of maturation index
- Assess VHI
- Assess VuHI
- Obtain vulvo-vaginal imaging (optional)
- Perform TVU and measure endometrial thickness
- Perform endometrial biopsy
- Obtain blood samples for safety laboratory tests, hormone levels, and serum markers of bone metabolism
- Obtain urine sample for urinalysis and urinary marker of bone metabolism
- Assess eDiary compliance. For subjects who received a device, it should be collected
- Assess study medication returned and assess compliance with study medication

8.4 Telephone Call at the End of the Follow-up Period (Two Weeks after Treatment Period Completion) Procedures

Subjects will receive a follow-up telephone call two weeks after the last dose of study drug. During the phone call the study personnel will assess for AEs since the last visit. Any AEs should be captured in the eCRF. If an AE is reported and needs to be followed, procedures described in Section 7.6.11 should be followed. Information of concomitant therapy after the last dose of study drug will also be collected in the phone call.

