- l May be omitted in subjects with a normal mammogram within 9 months prior to screening for which the results are available.
- m To be assessed based on pill count. When there is a discrepancy between the pill count and the subject-reported compliance, the subject-reported compliance should be used.
- n Do not perform if discontinuation (early termination) occurs PRIOR to VISIT 5 (Week 12).
- o Repeat after cure of infection at V1.

- p Repeat after cure of infection at V2.
- q Follow-up call should occur ON Day 14 after last dose. In case subject does not respond, three follow-up attempts should be made.

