7.5.11.2 Vaginal Infection

At all visits the sequence of procedures should follow Section 8. However, if a vaginal infection requiring medication (e.g. candida vaginitis) is identified at Visit 1 (screening) or at Visit 2 prior to randomization, the infection must be treated to resolution. After the vaginal infection is treated, 2 weeks (14 days) should be allowed to restore the local environment before continuing the screening or randomization procedures. The time necessary to treat the infection will not count against the 4-week duration of the screening period. If a vaginal infection is identified please follow these procedures:

1. If the vaginal infection is discovered during the gynecological examination (Visit 1 or Visit 2), the vaginal pH, the vaginal smear for maturation index, and the sample for cervical PAP, along with the rest of the remaining assessments for that visit, should not be conducted until the resolution of the infection is confirmed. The VVA questionnaire needs to be repeated as it should have been conducted before the gynecological examination.
2. If the infection is identified based on the results of cervical pap or vaginal smear for maturation index obtained at Visit 1, the infection should be treated until resolution. The patient should then return for an Unscheduled Visit (prior to Visit 2) for a repeat of the VVA questionnaire, gynecological examination, vaginal pH, vaginal smear (maturation index), and cervical pap, to confirm eligibility. If eligible based on these results the subject may continue to Visit 2.
3. If the infection takes longer than 30 days to treat, safety laboratory tests (hematology and chemistry) should be repeated at an Unscheduled Visit at the infection-free timepoint to confirm eligibility. If eligible based on these results the subject may continue to Visit 2 if the infection was diagnosed prior to Visit 2 or continue with the outstanding procedures from Visit 2 if the infection was diagnosed at Visit 2.
4. In the situations described in items 2 and 3 above, results of tests repeated between Visit 1 and Visit 2, at the infection-free timepoint, will be used to confirm eligibility (Visit 1) as well as baseline values (Visit 2) and do not need to be repeated again at Visit 2. The TVU, endometrial biopsy, and ECG do not need to be repeated even if they were assessed prior to the discovery of the infection.

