8. STUDY ACTIVITIES

The overall Schedule of Time and Events for this study is provided in Table 3.1-1.

Subjects will be required to participate in both on-site clinic visits as well as a phone call that site personnel will schedule based on the subject's initial randomization date. For the scheduled phone call, subjects will be contacted by the Investigator or designee at the end of the post-study Follow-up Period. If clinically indicated and at the Investigator's discretion, the study subject may be asked to complete an unscheduled visit.

In the sections below, activities to be performed have been listed in the order that appears to simplify the process for the site and the subject. At Screening and Randomization visits, procedures that may exclude a subject immediately are to be conducted earlier to ensure subjects that will not qualify do not undergo the most invasive/uncomfortable procedures.

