8.1 Screening, Visit 1 (Up to 4 Weeks Prior to Randomization)

Screening should take place up to 4 weeks (28 days) prior to randomization. Enough time between Visit 1 and Visit 2 should be allowed to receive the results of tests conducted as part of Visit 1, therefore, Visit 2 should not take place earlier than 1 week after Visit 1. The Investigator will inform each prospective subject of the nature of the study, explain the potential risks, and obtain written informed consent from the subject prior to performing any study-related procedures and prior to the administration of the study drug.

- Sign ICF
- Contact IxRS to obtain subject ID number
- Obtain urine sample for urinalysis (dipstick + central laboratory) and perform dipstick assessment prior to the next procedure
- Record demographics
- Record medical history
- Record prior therapy
- Assess inclusion and exclusion criteria
- Assessment of VVA symptoms
- Measure vital signs (BP, pulse rate, and oral temperature performed after subject is in seated or in a recumbent position ≥ 3 minutes) including height and weight
- Perform physical examination
- Perform breast examination
- Perform gynecological examination
- Measure vaginal pH
- Obtain vaginal smear for assessment of maturation index
- Obtain sample for cervical PAP smear

- Perform TVU and measure endometrial thickness
- Perform endometrial biopsy
- Obtain 12-lead ECG (performed in a supine position after ≥ 5 minutes)
- Obtain blood samples for safety laboratory tests and FSH to confirm postmenopausal status in women ≥ 45 years old who do not remember the date of the last spontaneous menstrual period OR women who had a hysterectomy without oophorectomy.
- Assess for AEs (with a start time after signing ICF)
- Conduct/order mammogram
For subjects who have a normal mammogram within 9 months prior to screening for which the results are available, those results can be used and a new mammogram is not required for eligibility assessment.

At the time of Screening, a one-time follow-up blood draw is allowed for the retest of abnormal values that may exclude the subject from study participation.

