10.3 Laboratory Evaluations

Safety laboratory tests shown in Table 7 will be conducted at screening, randomization, Week 12, and early termination before Visit 5 (hereafter ET).

Table 7 Safety Laboratory Tests

Category	Evaluation Items
Hematology Tests	hematocrit, hemoglobin, platelet count, red blood cell (RBC) count, white blood cell (WBC) count with differential (eosinophil count, basophil count, neutrophil count, monocyte count, lymphocyte count), platelet count, mean corpuscular hemoglobin (MCH), mean corpuscular hemoglobin concentration (MCHC), mean corpuscular volume (MCV), RBC distribution width (RDW), mean platelet volume (MPV)
Blood Chemistry Tests	ALP, ALT, AST, total bilirubin, GGT, LDH, BUN, creatinine, uric acid, sodium (Na), potassium (K), chloride (Cl), calcium (Ca), glucose, total protein
Lipids	Total cholesterol, low-density lipoprotein (LDL) cholesterol, very-low-density lipoprotein (VLDL) cholesterol, high-density lipoprotein (HDL) cholesterol, and triglycerides
Coagulation	Thromboplastin time, fibrinogen, antithrombin III, , protein-C, and protein-S
Urinalysis for Quantitative	pH, specific gravity
Urinalysis for Qualitative	Color, bilirubin, glucose, ketones, nitrite, occult blood, protein, microscopic evaluation of sediment, and urobilinogen

ALT = alanine aminotransferase; AST = aspartate aminotransferase; ALP = alkaline phosphatase; GGT = gamma-glutamyl transferase; LDH, lactate dehydrogenase; BUN, blood urea nitrogen

The measurements on safety laboratory evaluations will be handled as follows:

- 1) For quantitative scale items, summary statistics of measurements taken at baseline, Week 12 will be calculated by treatment group. The change from baseline to Week 12 will be also calculated by treatment group.
- 2) For qualitative scale items, frequencies for each category at baseline, Week 12 will be counted by treatment group.
- 3) For all laboratory analytes in Appendix 3, proportion of subjects who meet the predefined limits at any timepoints will be calculated. Difference in the incidence proportion among treatments and its 95% CI will be calculated. This analysis will be performed using data until Visit 5. The analysis will be applied to data taken at the last timepoint before stopping dosing until Visit 5.

The factor V Leiden will not be summarized.

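### Urine is listed after the pelvic procedures at Visit 5 and early termination but before them at baseline, so Week 12 occult blood, protein and sediment risk procedural contamination

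*Protocol*

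**What the plan says.** **Visit 1 (8.1).** Urine is the third item, before any examination: "Obtain urine sample for urinalysis (dipstick + central laboratory) and perform dipstick assessment prior to the next procedure".

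**Visit 2 (8.2), the baseline visit.** Urine is the second item: "Obtain urine sample for urinalysis, dipstick, and urine markers of bone metabolism. Dipstick assessment should be performed prior to the next procedure".

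**Visit 5 (8.3.2).** "Obtain urine sample for urinalysis and urinary marker of bone metabolism" comes near the end. It follows the gynecological examination, pH strip, smear, VHI and VuHI, optional imaging, transvaginal ultrasound (TVU), the item "Perform endometrial biopsy", and the blood draw.

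**Early termination (8.5).** The urine item has the same position and wording, but the list has no biopsy. Footnote n to the Schedule of Time and Events likewise rules out a biopsy when a subject stops before Visit 5.

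**Status of the order.** Section 7.5.11.2 states: "At all visits the sequence of procedures should follow Section 8". Section 8 explains that "activities to be performed have been listed in the order that appears to simplify the process for the site and the subject", and adds that steps able to exclude a subject come early at screening and randomization.

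**Use of the data.** SAP 10.3 lists occult blood, protein and sediment among the qualitative urinalysis items and says: "For qualitative scale items, frequencies for each category at baseline, Week 12 will be counted by treatment group". Under SAP 6.3 the baseline is the Visit 2 value, or the screening value if that is missing.

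**The concern.** A baseline and Week 12 tabulation is easiest to read when both samples are taken under like conditions. Here the baseline urine is voided before any pelvic contact. The Week 12 urine follows an examination, a smear, a TVU and, in women with a uterus, a suction biopsy.

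The protocol itself recognises the mechanism. Section 7.6.6 tells the investigator to consider a recent biopsy, another invasive procedure or atrophy as a source of vaginal bleeding. The VHI in Appendix 3 has grades for mucosa that bleeds on light contact or on scraping. Blood and cells from these sources could enter a voided sample.

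Three things are at stake:
- A rise in positive results from baseline to Week 12 could be partly an artefact of the visit.
- A real urinary difference between arms could be diluted.
- A false positive could lead to further testing. Section 7.6.11.7 treats a result that needs further diagnostic testing as clinically significant and to be considered for AE reporting.

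Week 12 (or early termination) is the only on-treatment urinalysis in the schedule, and only a telephone call follows. No later scheduled sample can settle a doubtful result.

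**Working it through.** The point rests on the order of procedures. The plan gives no figure to reproduce.

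**Step 1: the lists side by side**

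| Visit | Pelvic procedures before urine | Biopsy before urine |
|---|---|---|
| Visit 1 (8.1) | None | No (biopsy listed later) |
| Visit 2 (8.2) | None | No biopsy at this visit |
| Visit 5 (8.3.2) | Examination, pH strip, smear, TVU | Yes, if the uterus is intact; only the blood draw lies between |
| Early termination (8.5) | Examination, pH strip, smear, TVU | No biopsy before Visit 5 |

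**Step 2: who is exposed.** The smear applies to all subjects. The biopsy applies only to those with an intact uterus (7.6.5). Section 3.1 caps subjects without a uterus at 60%, so the share with a uterus, *u*, is at least 1 − 0.60 = 0.40. That is 0.40 × 600 = 240 or more of about 600 randomized.

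**Step 3: scale, for illustration.** Let *b* be the true positive rate and *q* the chance that the biopsy turns a negative sample positive. Neither is in the documents. I assume *b* = 5% and *q* = 10% to 50%. Contact bleeding from the smear is left out.

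Observed Week 12 rate = *b* + (1 − *b*) × *u* × *q*

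- *u* = 0.40, *q* = 0.10: 0.05 + 0.95 × 0.04 = 8.8%
- *u* = 0.40, *q* = 0.50: 0.05 + 0.95 × 0.20 = 24.0%
- *u* = 1.00, *q* = 0.10: 0.05 + 0.95 × 0.10 = 14.5%
- *u* = 1.00, *q* = 0.50: 0.05 + 0.95 × 0.50 = 52.5%

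**Step 4: effect on an arm difference.** With the same *u* and *q* in both arms, the observed difference is the true difference × (1 − *u* × *q*). It keeps 96% to 80% of its size when *u* = 0.40, and 90% to 50% when *u* = 1.00. Equal contamination therefore shrinks a difference and does not create one.

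**Step 5: what is analysed.** SAP 10.3 item 2 counts categories by arm. The differences with confidence intervals in item 3 apply to the analytes in SAP Appendix 3, which has no urinalysis item. No test or interval is planned for these data.

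**The case against.** The early urine step at Visits 1 and 2 has its own purpose. The dipstick screens for urinary tract infection, which must be treated before efficacy assessments (7.5.11.1), and Visit 5 has no dipstick. Collection technique is left to a laboratory manual (7.6.10.2) that is not among the documents and may deal with contamination. Reporting an AE is a matter of investigator judgement, and the investigator takes the biopsy and knows of it. All of this stands, and it limits how serious the point is. It does not explain why urine should come last at Visit 5, and it does not make the two samples alike.

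A reader might infer three stronger things that the documents do not support:

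- **That the Week 12 samples are contaminated.** No contamination rate appears anywhere. The documents show a risk only. The biopsy part is absent in women without a uterus and at early termination before Visit 5.
- **That the arms are biased against each other.** Both arms follow the same order. If ospemifene reduces mucosal friability, contact bleeding could be rarer on active treatment. For example, 20% contamination on placebo against 10% on ospemifene would give a spurious 0.95 × (0.20 − 0.10) = 9.5 points at 5% true positivity. Those rates are invented for the example, and nothing in the documents establishes such a gap.
- **That the trial loses power.** No test of urinalysis is planned, so no planned power figure changes.

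Urinary deoxypyridinoline, a bone marker, is collected in the same step. The documents give no reason why its position in the visit should affect it.

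**Conclusion.** The difference in order is certain from the text, and 7.5.11.2 makes it an instruction, though one worded as a recommendation. It puts Week 12 occult blood, protein and sediment at a risk of contamination that the baseline sample does not carry. The descriptive comparison in SAP 10.3 is weaker for it.

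The size cannot be known from the documents. The figures above depend wholly on the assumed 5% true rate and the assumed 10% to 50% conversion; only the 40% minimum uterus share comes from the plan. The likely harms are a distorted change from baseline, some dilution of any true arm difference, and avoidable follow-up of false positives. This is a limited safety-data matter: it touches no primary or secondary efficacy endpoint. It is worth correcting because the artefact is avoidable.

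**What to change.** In Protocol 8.3.2 and 8.5, move the urine-collection step ahead of the gynecological examination, pH strip, smear, TVU and (at Visit 5) biopsy, so that it matches 8.1 and 8.2.

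For samples already collected, identify subjects with a biopsy on the day of the Week 12 urine sample, and interpret occult blood, protein and sediment with that caveat. The protocol asks for the date of specimen collection and not the time (7.6.10.1, 7.6.5). The data can therefore show a same-day biopsy, but not whether urine came before or after it.

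The cost is one moved line in each of two visit lists, a small change in visit flow, and a note to the urinalysis table. No procedure, visit or subject is added.

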8.5 Early Termination Procedures

If a subject discontinues from the study early (i.e., before end of treatment period Visit 5), the following measurements and/or evaluations will be made and recorded in the eCRF:

- Record concomitant therapy
- Assess for AEs
- Assess symptoms of VVA
- Assess FSFI
- Assess UDI-6

- Measure vital signs (BP, pulse rate, and oral temperature performed after subject is in seated or in a recumbent position ≥ 3 minutes) including weight
- Perform physical examination
- Perform breast examination
- Perform gynecological examination
- Measure vaginal pH
- Obtain vaginal smear for assessment of maturation index
- Assess VHI
- Assess VuHI
- Obtain vulvo-vaginal imaging (optional)
- Perform TVU and measure endometrial thickness. Capture images to be sent to the central reader
- Obtain blood samples for safety laboratory tests, hormone levels and serum markers of bone metabolism
- Obtain urine sample for urinalysis and urinary marker of bone metabolism
- Assess study medication returned and assess compliance with study medication
- Assess eDiary compliance. For subjects who received a device, it should be collected

9. PLANNED STATISTICAL METHODS

9.1 General Considerations

The statistical analysis will be performed by the Sponsor or designee. Detailed statistical analysis methods will be specified in a statistical analysis plan (SAP) according to this section of the study protocol. Analyses deviating from those outlined in the protocol will be clearly specified in the SAP, and the reason for deviation from the protocol will be described. The SAP will be finalized before breaking the study blind.

Unless otherwise noted, continuous variables will be summarized by using the number of non-missing observations, arithmetic mean, standard deviation (SD), median, minimum, and maximum values as descriptive statistics; categorical variables will be summarized by using the frequency count and the percentage of subjects in each category as descriptive statistics.

All statistical tests will be performed at the 0.05 significance level using two-sided tests, except where otherwise noted.

All subject study data, including data not appearing in tables, will be presented by-subject data listings. In general, all tables will be presented by treatment group. Individual subject data and any derived data will be presented by treatment and subject. All analyses and tabulations will be performed by using SAS® Version 9.2 or higher.

9.2 Determination of Sample Size

Approximately 600 subjects, about 300 subjects per arm (1:1 randomization ratio), will be randomized in the study.

Table 9.2-1 shows the difference between ospemifene and placebo and the effect size in each of 4 co-primary endpoints, namely vaginal pH, percentage of parabasal cells and percentage of superficial cells in the maturation index of the vaginal smear, and MBS of vaginal dryness for the two pivotal studies.

Table 9.2-1 Change from Baseline to Week12 in Two Pivotal Studies

| Primary Efficacy Variable | Study | Ospemifene | Placebo | Difference | SDcommon | Effect Size ^{*2)} |
|---------------------------|----------|-------------|---------|------------|----------|----------------------------|
| MBS of Vaginal Dryness | 15-50310 | C P I | | | | |
| | 15-50821 | | | | | |
| Vaginal pH | 15-50310 | | | | | |
| | 15-50821 | | | | | |
| % Parabasal Cells | 15-50310 | | | | | |
| | 15-50821 | | | | | |
| % Superficial Cells | 15-50310 | | | | | |
| | 15-50821 | | | | | |

*1) Mean±SD

*2) Effect size = $\frac{\text{Difference}}{\text{SDcommon}}$; SDcommon = $\sqrt{\text{SD}_{\text{Ospemifene}}^2 + \text{SD}_{\text{Placebo}}^2}$

For the planned study, referring to the results in

Table 9.2-1, the effect size is assumed to be 0.27 for MBS of vaginal dryness, 0.70 for vaginal pH, 0.83 for % parabasal cells and 0.68 for % superficial cells. Table 9.2-2 shows the power of two-sided t-test with significance level of 0.05 and total sample size of 600 (300 for each treatment group) for each of the 4 co-primary endpoints under the assumed effect size. A sample size of 600 patients provides $\geq 90\%$ power to assess the 4 co-primary efficacy endpoints.

Table 9.2-2 Expected Power with Total Sample Size of 600

| | MBS of Vaginal Dryness | Vaginal pH | % Parabasal Cells | % Superficial Cells | 4 Co-Primary Endpoints |
|-------------|------------------------|------------|-------------------|---------------------|------------------------|
| Effect Size | | | | | C P1 |
| Power | | | | | |

